## SUMMARY

Title	BIO-Precision Study
Descriptor	Assessment of the utility of BIOMONITOR to identify AF in ablation candidates using precise AF detection
Design	Prospective, multicenter, observational study
Purpose	The purpose of this study is to evaluate the diagnostic utility of BIOTRONIK's subcutaneous cardiac rhythm monitor (SCRM) for the detection of AF prior to an ablation procedure.
Subject Population	Study population includes patients diagnosed with paroxysmal AF being evaluated for an AF ablation.
Sample Size	This study will enroll up to 100 subjects, to obtain 60 usable Holter recordings.
Clinical Sites	Up to 5 U.S. sites.
Follow-up Period	All subjects will be followed for three months post 48 hr Holter monitoring.
Primary Objective	The primary objective of this study is to determine the diagnostic utility of the BIOMONITOR to detect AF within study subjects who are being evaluated for an ablation. Specifically, the diagnostic sensitivity of the BIOMONITOR will be determined by comparing AF events detected by the BIOMONITOR and 48 hr Holter monitor for each subject. Using the 48 hr Holter monitor as the gold standard, subjects with AF events detected by the BIOMONITOR will be categorized as true positive or false positive.
Study Risk Determination	Standard of care study including market released devices implanted according to FDA approved indications for use.
Sponsor	BIOTRONIK, Inc. Clinical Studies Department [name]

## 1. INTRODUCTION

### 1.1 Study Overview

BIO-Precision is a post-market study investigating the utility of atrial fibrillation (AF) detection using BIOTRONIK's subcutaneous cardiac rhythm monitor (SCRM). The purpose of this study is to evaluate the diagnostic utility of BIOTRONIK's SCRM for the detection and confirmation of AF prior to an ablation procedure. Study population includes patients with paroxysmal AF being evaluated for an AF ablation. This study will enroll up to 100 subjects, to obtain 60 usable Holter recordings, at 5 study sites within the United States (U.S.). Study subjects will be followed for three months after the completion of a 48 hr Holter monitor.

### 1.2 Background

SCRMs are devices capable of long-term cardiac rhythm monitoring. These devices are commonly used to assist in the diagnosis of unexplained palpitations and syncope. SCRM provide more reliable and accurate monitoring than a routine surface ECG and can provide continuous long term monitoring compared to Holter monitoring. A growing use of SCRM is for the detection and management of AF, in particular in patients with high thromboembolic risk. SCRM were originally designed after pacemaker technology, however, current SCRM have significantly decreased profiles, allowing for less-invasive insertion procedures and low complication rates, making them a safe and efficient option for arrhythmia diagnosis.

Atrial fibrillation is the most common diagnosed arrhythmia, and it is estimated to effect 6-12 million people in the U.S. by 2050. AF has many causes and can be both symptomatic and asymptomatic, and is associated with an increase in hospitalizations, stroke, and heart failure. Recent studies have suggested that the adverse effects of AF may be correlated with AF episode duration; therefore it is important to appropriately capture AF episodes and their durations to adequately treat patients and reduce their AF burden. AF can be diagnosed through medical history, exam, and a surface ECG; however, for non-sustained or paroxysmal AF, a surface ECG may not be sufficient to accurately detect the patient's true AF burden. Therefore, the use of a SCRM may result in precise and accurate AF detection over a longer period of time as compared to traditional surface (e.g. Holter) monitors.

Recent guidelines recommend AF ablation in patients with symptomatic AF, refractory or intolerant to at least one Class 1 or 3 antiarrhythmic medication. Asymptomatic patients may choose to pursue an AF ablation as an alternative to continuous, long-term anticoagulation therapy. ECG monitoring is recommended pre- and post AF ablation procedure. Prior to undergoing an ablation, it is important for the physician to confirm the presence of AF as well as the current AF burden. Available methods for ECG monitoring, as discussed above, range from in office ECG, Holter (24 hours to 7 days), or SCRM (up to 4 years of continuous arrhythmia monitoring). Not only are SCRM valuable for detecting AF and AF burden prior to ablation, they may also provide important data post-ablation in

assisting the physician in determining the success rate of the ablation procedure. The focus of this study is to determine the utility of SCRMs for AF detection in patients who are being evaluated for an ablation.

### 1.2.1 BioMonitor Single-center AF Detect Study

BIOTRONIK conducted an AF Detection clinical study in order to assess the performance of the BioMonitor AF feature in clinical practice. This study used BIOTRONIK's first generation SCRM, which received FDA approval on June 2, 2014 (510(k) number: K132960). The ability of BioMonitor to detect episodes of AF was quantified in comparison with the gold-standard, expert-annotated, external Holter ECG recorder. Sixty six (66) participants with suspected paroxysmal or persistent atrial fibrillation who had been implanted with a BioMonitor were additionally equipped with an external Holter ECG recorder.

The main aim of the AF Detect study was to record surface electrocardiograms (ECG) to reference it with the subcutaneous ECG of the BioMonitor. For this reason a Holter ECG device was applied, and the patient was asked to come back after 2 days. All episodes were interrogated and a memory dump was conducted. The site was equipped with the long-term three channel Holter ECG system "LifeCard" from the company "Spacelabs Healthcare" ([www.spacelabshealthcare.com](http://www.spacelabshealthcare.com)). This is a CE-approved compact Holter Ambulatory ECG Recorder that is capable of storing a continuous, 48-hour recording of up to 3 leads onto a Compact Flash (CF) card. Lifecard ECG was used to establish an independent assessment of AF, and represents the gold standard for AF detection. The LifeCard ECGs were manually annotated for AF episode onset and termination, and the annotations were verified by an independent ECG reviewer.

The surface ECG of the Holter ECG and the subcutaneous ECG of the BioMonitor were synchronized by time and date and manually assessed to determine the AF detection performance. Furthermore, automatically detected arrhythmias were assessed and documented. BioMonitor and LifeCard AF episodes were directly compared to one another on an episode-by-episode basis, by which each episode longer than 2 minutes in duration (default BioMonitor confirmation window) was classified as true positive (TP), false positive (FP), or false negative (FN).

Of the 66 participants in AF Detect, 39 showed at least one true AF episode during the 48-hour Holter period, with a maximum of 30 distinct, true AF episodes experienced by one subject. A total of 146 AF episodes were annotated from 2878 hours of Holter ECG data. During the execution of the AF Detection study, three subjects had missing Holter data, and hence were excluded from the analysis. The primary endpoint analysis determined an AF detection sensitivity of  $95.4\% \pm 13.3\%$  and a positive predictive value of  $76.3\% \pm 38.7\%$ .

## 1.3 System Description

This study utilizes BIOTRONIK's subcutaneous cardiac rhythm monitor (SCRM).

The BIOMONITOR is a SCRM that continuously monitors the heart rhythm. BIOMONITOR programming and data collection during insertion and follow-up are performed with a portable BIOTRONIK programmer. Additionally, the Home Monitoring feature enables physicians to perform remote diagnosis management over the lifetime of the device.

The BIOMONITOR records automatically the occurrence of certain cardiac arrhythmias.

The BIOMONITOR is indicated to detect the following cardiac arrhythmias:

- Atrial fibrillation
- Bradycardia
- Sudden rate drop
- High ventricular rate (HVR)
- Asystole

Devices included in the clinical study:

- BioMonitor 2 (FDA clearance April 11, 2016; K152995 number) or FDA cleared successor (hereafter, referred to as BIOMONITOR)

[figure not shown]
The BIOMONITOR is to be used with the following components:

- BIOTRONIK Renamic or ICS 3000 programmer or FDA-cleared successor with the most recent software and later corresponding software updates

Subjects inserted with a BIOMONITOR will be remotely monitored with BIOTRONIK's Home Monitoring® system and will be provided a BIOTRONIK CardioMessenger II, II-S or FDA-cleared successor. The BIOTRONIK Remote Assistant may also be provided and allows manual triggering of an ECG recording by the patient.

### 1.3.1 BIOTRONIK Home Monitoring® with daily sECGs

The BIOTRONIK Home Monitoring® system provides early detection of arrhythmic events such as high ventricular rates and of silent, asymptomatic events like atrial fibrillation (Figure 1), through the transmission of detection and termination snapshots of the indicated event. Transmissions include both periodic and triggered subcutaneous electrocardiogram (sECG) recordings.

**Figure 1: Atrial Fibrillation sECG Transmission Example**

[figure not shown]
The BIOMONITOR has the capability to transmit messages including sECG signals to the BIOTRONIK Home Monitoring® Service Center daily so that the monitoring physician will have updated data on the technical and physiological parameters of the patient every 24 hours. BIOTRONIK Home Monitoring® can be used to provide the physician with advance reports from the BIOMONITOR and can process them into graphical and tabular format.

## 2. STUDY DESIGN

The BIO-Precision study is a post-market, multicenter, prospective, observational study designed to evaluate AF detection performance of BIOTRONIK's SCRM, BIOMONITOR. Up to 100 subjects will be enrolled to collect a total of 60 usable Holter recordings. The subject population includes patients that are diagnosed with paroxysmal AF and are being evaluated for an AF ablation procedure. Study subjects will be enrolled at up to 5 participating U.S. sites. Subjects will be followed for three months after the completion of 48 hr Holter monitoring.

Potential subjects will be identified by the investigator from their general patient population and must have an approved indication for continuous arrhythmia monitoring with an SCRM according to local regulations. Subjects will be consented no more than 14 days prior to the insertion procedure (Figure 2) and screened to ensure they meet all of the inclusion and none of the exclusion criteria. Subjects may also be screened and consented up to 30 days following the insertion of a BIOMONITOR (Figure 2). All subjects will be considered 'provisionally enrolled' until they initiate the 48 hr Holter monitoring, at which time they are considered fully enrolled.

For subjects with an existing BIOMONITOR, a pre-Holter observation period will be initiated at enrollment (Figure 2). This observation period should be 12-16 days in duration and will allow for characterization of the BIOMONITOR performance prior to Holter monitoring. Following this observation period, Holter monitoring should be initiated within 7 days. For subjects consented before BIOMONITOR insertion, the insertion procedure should be completed within 14 days, followed by the pre-Holter observation period (Figure 2). Holter monitoring should be initiated within 7 days after the completion of the observation period.

[figure not shown]

**Figure 2: Enrollment Pre- and Post-BIOMONITOR insertion**

The primary analysis will focus on the utility of the BIOMONITOR for the detection of AF within patients who are being evaluated for an ablation. Data will be collected from in-person visits at study enrollment, BIOMONITOR insertion, and initiation and completion of 48 hr Holter monitoring. In addition, BIOMONITOR performance data will be collected throughout the study duration using BIOTRONIK Home Monitoring®, including a required Home Monitoring data check at the end of the pre-Holter observation period. Holter monitor recordings will be evaluated by a Holter Core Laboratory. In addition, BIOMONITOR detections may be adjudicated by an event adjudication committee, if applicable.

Figure 3 provides an overview of the clinical study design. Details of subject eligibility requirements are noted in Section 3.2.2 and details of other study specific procedures and data collection are noted in Section 3.2 and Section 4.

**Figure 3: BIO-Precision Study Design Flowchart**

## 2.1 Study Objectives

This study includes the assessment of one primary objective related to the diagnostic utility of the BIOMONITOR to detect AF prior to an ablation procedure. Additional data of interest will be collected and assessed.

### 2.1.1 Primary Objective

The primary objective of this study is to determine the diagnostic utility of the BIOMONITOR to detect AF within study subjects who are being evaluated for an ablation. Specifically, the diagnostic sensitivity of the BIOMONITOR will be determined by comparing AF events detected by the BIOMONITOR and 48 hr Holter monitor for each subject. Using the 48 hr Holter monitor as the gold standard, subjects with AF events detected by the BIOMONITOR will be categorized as true positive or false positive.

It is expected that sensitivity will be greater than 90% in detecting AF within study subjects that are being evaluated for ablations.

Diagnostic Sensitivity:

$H_0$ : The Sensitivity (Se) for detecting at least one true positive AF episode per subject will be less than or equal to 90%. ( $Se \leq 90\%$ )

$H_a$ : The Sensitivity for detecting at least one true positive AF episode per subject will be greater than 90% ( $Se > 90\%$ )

A rejection of the null hypothesis would demonstrate that there is evidence that Sensitivity is greater than 90%.

### 2.1.2 Additional Data of Interest

Additional information will be collected to characterize the study population, BIOMONITOR usage, and progress of the study. Specifically, data of interest will include:

- Baseline demographics, including age, gender, height, weight, race and ethnicity (optional)
- Medical history
- Cardiovascular medication
- Insertion procedure information, including success/failure of insertion, procedure times, location and orientation of the BIOMONITOR, and reason for insertion. Data may be collected retrospectively if insertion occurred prior to enrollment.
- Inserted device information, including model, serial number, and insertion date
- Ablation procedure information, including date of ablation and the utility of the BIOMONITOR in determining ablation candidates

- Compliance to protocol requirements and study visit schedule
- Success of Home Monitoring transmissions
- BIOMONITOR performance during the study including, but not limited to, R-wave amplitude and arrhythmia detections as reported using BIOTRONIK Home Monitoring®
- AF episodes as detected by the Holter monitor and BIOMONITOR, as well as additional arrhythmic episodes. AF detections will be used to support patient, episode, and duration metrics including sensitivity, specificity, positive predictive value, and negative predictive value of the BIOMONITOR.
- Visibility of P-waves from recorded BIOMONITOR episodes
- AF episodes within the pre-Holter observation period

## 2.2 Subject Status Definitions

The subject status definitions utilized in this study are provided in Table 1.

**Table 1: Subject Status Definitions**

Subject Status	Definition
Provisionally Enrolled	
Subject has provided written informed consent but has not initiated 48 hr Holter monitoring.
 
Provisionally enrolled subjects that initiate 48 hr Holter monitoring will be considered fully enrolled.
 
Provisionally enrolled subjects that do not initiate 48 hr Holter monitoring will be exited. These subjects will be included in the additional data of interest analysis population.

Screen Failure	
Subject has signed consent, but at the time of consent it was identified the subject does not meet all inclusion/exclusion criteria
 
OR
 
Subject consented prior to insertion, but exited prior to insertion or does not receive a BIOMONITOR.
 
Subject will be exited and will not be included in the analysis population.

Enrolled	
Subject has met all inclusion and exclusion criteria, provided written informed consent, successfully inserted with a BIOMONITOR, and initiates 48 hr Holter monitoring.
 
Subject will be included in the analysis population.

## 2.3 Study Size and Duration

During this study, data will be gathered, analyzed, and reported to evaluate the diagnostic utility of the BIOMONITOR. It is anticipated that up to 100 subjects will be enrolled to have 60 subjects who will complete 48 hr Holter monitoring and will be followed for three months post 48 hr Holter monitoring at up to 5 U.S. sites.

## 2.4 Sample-Size Analysis

The study is designed to limit the number of subjects involved while still exposing the device to a sufficiently large subject population to evaluate the utility of BIOMONITOR in subjects that are being evaluated for AF ablation. A sample size of 60 subjects with evaluable data sets is required to evaluate the diagnostic sensitivity with the following assumptions:

- Prevalence of AF during Holter test: 50%
- Confidence interval: 95%
- Precision level: 6.35%
- Expected patient-based sensitivity: 97%
- Drop-out rate after 48 hr Holter monitoring is initiated: 8%

To account for expected attrition due to subject withdrawal following consent but prior to completion of the study testing period:

- Up to 100 subjects will be provisionally enrolled
- Assumed 40% drop out rate between consent and the initiation of 48 hr Holter monitoring (e.g. R-wave amplitude <0.25 mV, no AF detection during pre-Holter observation period, withdrawn consent, etc.)
- Sixty subjects will undergo 48 hr Holter monitoring (fully enrolled)

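### Section 2.4 uses 60 both for evaluable data sets and for Holter starts; its own inputs fit only starts, with about 55 to 56 evaluable

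*Protocol*

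**What the plan says.** Section 2.4 opens with the requirement: "A sample size of 60 subjects with evaluable data sets is required to evaluate the diagnostic sensitivity with the following assumptions". Its list of assumptions gives AF prevalence during the Holter of 50%, a 95% confidence interval, precision of 6.35%, expected patient-based sensitivity of 97%, and "Drop-out rate after 48 hr Holter monitoring is initiated: 8" per cent. It then allows up to 100 provisional enrolments, assumes 40% are lost between consent and Holter start, and concludes: "Sixty subjects will undergo 48 hr Holter monitoring (fully enrolled").

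Table 1 in section 2.2 fixes what fully enrolled means: "Provisionally enrolled subjects that initiate 48 hr Holter monitoring will be considered fully enrolled". It is a status gained at the start of recording, not at its end.

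Elsewhere the same 60 is given as an end product:
- Summary: "This study will enroll up to 100 subjects, to obtain 60 usable Holter recordings".
- Section 1.1: "to obtain 60 usable Holter recordings, at 5 study sites within the United States".
- Section 2: "Up to 100 subjects will be enrolled to collect a total of 60 usable Holter recordings".
- Section 2.3: "up to 100 subjects will be enrolled to have 60 subjects who will complete 48 hr Holter monitoring".

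Section 2.5.3 limits the primary analysis to enrolled subjects with both evaluable Holter data and evaluable BIOMONITOR data, so starting and being evaluable are different things in this protocol.

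**The concern.** One number stands at two points of the subject flow that are separated by an assumed 8% loss. If 60 start and 8% are lost, fewer than 60 are evaluable. If 60 must be evaluable, more than 60 must start.

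Two things are at stake. First, the section does not say when recruitment is complete: at 60 Holter starts, as the end of 2.4 has it, or at 60 usable recordings, as the Summary and sections 1.1 and 2 have it. Second, a reader who takes 60 evaluable at face value will expect 30 AF-positive subjects behind the primary sensitivity estimate, whereas the protocol's own rates lead to about 28.

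**Working it through.** **Inputs, all from section 2.4:** Se = 0.97; half-width d = 0.0635; 95% confidence, taken as two-sided (z = 1.96); prevalence 0.50; loss after Holter start 0.08; loss before Holter start 0.40; cap of 100 consents. No formula is printed. The usual precision formula for a proportion, scaled by prevalence, is assumed.

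**Reproducing the 60**
1. AF-positive needed: z² × Se × (1 − Se) / d² = 1.96² × 0.97 × 0.03 / 0.0635² = 27.7.
2. Evaluable needed: 27.7 / 0.50 = 55.4. In whole subjects this is 28 AF-positive and 56 evaluable.
3. Starts needed: 55.4 / 0.92 = 60.3, or from whole subjects 56 / 0.92 = 60.9. That is 60 to 61.

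The figure 60 appears at step 3, not at step 2. With a one-sided z of 1.645 the results are 39.1 evaluable and 42.4 starts, and neither is 60. The inputs therefore place 60 at Holter starts.

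**Running the planned flow forward**
- 100 × 0.60 = 60 starts.
- 60 × 0.92 = 55.2 evaluable.
- 55.2 × 0.50 = 27.6 AF-positive.
- Half-width: 1.96 × √(0.0291 / 27.6) = 6.36%, against the stated 6.35%.

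**How far the yield depends on what the 8% covers.** Let r be the share of that loss which leaves usable Holter data or is recovered. The protocol gives no value, so r is shown over its full range. Evaluable = 60 × (1 − 0.08 × (1 − r)).

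| r | Evaluable | AF-positive | Half-width |
|---|---|---|---|
| 0 | 55.2 | 27.6 | 6.36% |
| 0.5 | 57.6 | 28.8 | 6.23% |
| 1 | 60 | 30 | 6.10% |

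**If 60 evaluable is really intended, with r = 0**
- Starts: 60 / 0.92 = 65.2, so 66.
- Consents: 60 / (0.92 × 0.60) = 108.7, so 109; rounding starts up first gives 66 / 0.60 = 110.
- Both exceed the cap of 100.

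**Secondary note on the primary test.** Section 2.5.1 specifies a one-tailed binomial test against 90% but the protocol states no alpha. Assume one-sided 0.05 and Holter-AF-positive subjects as denominator (the formula printed in 2.5.1 divides by TP + FP instead). If every AF-positive subject is detected, p = 0.9²⁸ = 0.052 for 28 of 28 and 0.9³⁰ = 0.042 for 30 of 30. Averaged over the random AF-positive count at 50% prevalence and Se 97%, power is about 15% with 55 evaluable and 24% with 60. At one-sided 0.025 it is about 0.5% and 2.5%.

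**The case against.** The strongest reply is that nothing is short. The 8% is already inside the 60, the required 55.4 evaluable subjects are what 60 starts deliver, and the precision target moves by 0.01 percentage points. This stands. A reader might infer from the mismatch that the study is too small for its stated precision; the arithmetic does not support that. It leaves the printed evaluable count wrong all the same.

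A second reply is that the 8% may not cost Holter data. It could be loss during the three-month follow-up, and section 3.3 allows data up to exit to be used. Sections 2.5.3 and 3.2.7 also allow a repeat Holter. Table 1 says enrolled subjects enter the analysis population, although 2.5.3 then narrows that to those with evaluable data. This stands as a limit: 55 is an expected value at r = 0, the yield could reach 60, and it would fall below 55 if incomplete BIOMONITOR data came on top of the 8%. It does not rescue the section. If the 8% is pure follow-up loss, it has no place in the sample-size inputs, which then give 55 to 56 and not 60.

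A tempting stronger reading is that the label decides whether the primary test can reject at all, because 28 of 28 narrowly misses 0.05 and 30 of 30 does not. The protocol does not support this. The alpha is assumed, the denominator is not the printed one, the AF-positive count is random, and power is low under either label. Weak power is a separate matter from the double use of 60.

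**Conclusion.** The point holds as a labelling error with a numerical consequence. On the protocol's own inputs, 60 is the number of Holter starts. The evaluable number is 55.4 required (56 in whole subjects) and 55.2 expected, with about 28 AF-positive. The overstatement is thus about 4 to 5 evaluable subjects and about 2 AF-positive subjects. Precision is essentially unaffected.

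This rests on an inferred formula, which reproduces 60 only at the starts, and on the 8% costing Holter data, which the protocol does not say. The contradiction within section 2.4 needs neither the formula nor a value for r; it arises as soon as any of the 8% reduces the evaluable set. The correction should be made because the same figure governs when recruitment is complete.

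**What to change.** 1. In section 2.4, state that about 56 evaluable data sets (about 28 Holter-AF-positive) are required for 6.35% precision, and that 60 to 61 subjects must initiate the Holter to allow for 8% loss.
2. In the same place, say what the 8% covers: unusable Holter or BIOMONITOR data, loss in the three-month follow-up, or both, and whether repeat Holters are netted against it.
3. Align the Summary and sections 1.1, 2 and 2.3, so that 60 is everywhere the number who initiate monitoring.
4. If 60 evaluable is truly intended, say instead that the 2.4 flow does not deliver it without recovery. It needs about 66 starts and about 109 to 110 consents at 40% attrition, so the cap of 100 must be reconsidered. The 40% should change only on evidence, not to fit the cap.

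Under items 1 to 3 the cost is wording in five places and one definition, with no change to conduct. Item 4 would mean revising the flow figures and the cap.

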### 2.5.1 Objective Analysis

The primary objective analysis will calculate the diagnostic sensitivity of the BIOMONITOR. Diagnostic sensitivity is the ability of the BIOMONITOR to correctly identify subjects who have AF as determined by the Holter monitor.

Specifically, diagnostic sensitivity is determined as:

$$\text{Diagnostic sensitivity} = \frac{\text{Number of TP patients}}{\text{Number of TP} + \text{Number of FP patients}}$$

Where TP is true positive and FP is false positive.

To test the primary hypotheses, sensitivity will be calculated and a one-tailed binomial test will be implemented to determine if there is evidence to support the rejection of the null hypothesis.

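### Section 2.4 reaches 60 subjects from a normal-approximation interval width; with about 28 to 30 AF-positive subjects that precision does not hold, and the one-tailed test that decides the primary objective has low power

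*Protocol*

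**What the plan says.** Section 2.4 of the protocol states that "A sample size of 60 subjects with evaluable data sets is required to evaluate the diagnostic sensitivity". The assumptions it lists are a 95% confidence interval, "Precision level: 6.35" (per cent), "Prevalence of AF during Holter test: 50" (per cent), "Expected patient-based sensitivity: 97" (per cent) and "Drop-out rate after 48 hr Holter monitoring is initiated: 8" (per cent). It gives no null value and no power. The same section also makes sixty the number who undergo Holter monitoring.

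Section 2.1.1 sets the null hypothesis that sensitivity is at most 90%, and adds: "A rejection of the null hypothesis would demonstrate that there is evidence that Sensitivity is greater than 90" (per cent). Section 2.5.1 says that "sensitivity will be calculated and a one-tailed binomial test will be implemented". It describes the quantity in words: "Diagnostic sensitivity is the ability of the BIOMONITOR to correctly identify subjects who have AF as determined by the Holter monitor".

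**The concern.** The sample size answers how wide a confidence interval would be. The primary objective asks whether sensitivity can be shown to exceed 90%. A size that suits the first question need not suit the second, and here only about half of the subjects are expected to enter the denominator.

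The stated width is doubtful too. The normal approximation is poor for a proportion of 97% in fewer than 30 subjects, where less than one missed subject is expected.

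At stake is how the primary result will be read. If a device that performs as expected will probably not reject the null hypothesis, non-rejection says little about the device. A reader of 2.4 would not know this, and would also expect a tighter estimate than the data can give.

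**Working it through.** **Inputs.** From 2.4: sensitivity 0.97, precision 0.0635, 95% confidence, prevalence 0.50, drop-out 0.08. From 2.1.1: null value 0.90. From 2.5.1: one-tailed binomial test.

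**Assumptions where the protocol fixes nothing or is ambiguous**
- Alpha: one-sided 0.05, with 0.025 and 0.10 as the range.
- Test: exact, with the z-test (no continuity correction) and mid-p as checks.
- Evaluable subjects: 60, or 55 if the 8% comes off the sixty who undergo Holter monitoring (60 × 0.92 = 55.2).
- Prevalence: 50% as stated, ranged to 70%. Section 1.2.1 reports 39 subjects with AF among 66, three of whom had no Holter data (39/63 = 61.9%). Section 3.1.4 also removes subjects with no AF in the observation period.
- Denominator: Holter-AF-positive subjects, as the text of 2.5.1 describes. The printed formula there is a separate matter.

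**Step 1: reproduce 60.**
- AF-positive subjects: 1.96² × 0.97 × 0.03 / 0.0635² = 27.7.
- Divide by prevalence: 27.7 / 0.50 = 55.4.
- Divide by retention: 55.4 / 0.92 = 60.3, against the stated 60.

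A one-sided 1.645 gives 42, and reading 6.35% as the full width gives 241. So 60 is a two-sided half-width, and 0.90 is not needed to obtain it.

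**Step 2: the precision delivered at 97% sensitivity.** The normal-approximation half-width taken at exactly 0.97 is 6.3 points with 28 AF-positive subjects and 6.1 with 30. When every subject is detected, however, that interval collapses to a point at 100% and misses 97%. The chance of this is 0.97^28 = 0.426 or 0.97^30 = 0.401. Actual coverage of the nominal 95% interval is therefore only about 57% (28) to 60% (30).

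Averaged over the binomial outcomes, in percentage points:

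| Interval | Half-width, 28 | Half-width, 30 | Lower arm, 28 | Lower arm, 30 |
|---|---|---|---|---|
| Exact (Clopper-Pearson) | 8.4 | 8.0 | 14.1 | 13.4 |
| Wilson | 7.9 | 7.6 | 13.6 | 12.9 |

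Even 30 of 30 gives an exact lower limit of 0.025^(1/30) = 88.4%.

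**Step 3: power of the test.** For k AF-positive subjects, the exact test rejects at the smallest r with P(X ≥ r | 0.90) ≤ alpha, and its power is P(X ≥ r | 0.97). Since 0.9^28 = 0.0523 and 0.9^29 = 0.0471, at least 29 AF-positive subjects are needed before rejection at 0.05 is possible. With exactly 30, all must be detected, and power is 0.97^30 = 40%.

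The count k is itself random, so power is averaged: sum over k of C(N,k) π^k (1−π)^(N−k) × power(k), where π is the prevalence and N the evaluable number. Each cell below gives 60 evaluable / 55 evaluable:

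| Test, one-sided alpha | 50% | 60% | 61.9% | 70% |
|---|---|---|---|---|
| Exact, 0.05 | 24% / 15% | 33% / 32% | 32% / 33% | 34% / 32% |
| z-test, 0.05 | 37% / 33% | 36% / 37% | 37% / 36% | 48% / 38% |
| Mid-p, 0.05 | 40% / 41% | 40% / 38% | 42% / 38% | 55% / 45% |
| Exact, 0.025 | 2.5% / 0.5% | 17% / 8% | 20% / 11% | 27% / 24% |
| Exact, 0.10 | 41% / 41% | 46% / 41% | 49% / 42% | 60% / 54% |

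At one-sided 0.10 the z-test and mid-p reach 49% to 53% at 50% prevalence and 62% to 68% at 60% to 70%. For the exact test at 0.05, no AF-positive count up to 60 gives more than 60% power.

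**The case against.** Sizing for precision is legitimate, and 2.4 reproduces its own 60, so a reader who infers an arithmetic error would be wrong. The fault is a mismatch between sizing criterion and primary test.

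A reader might also infer that the test was overlooked when 60 was chosen, or the opposite: 97 − 6.35 = 90.65, just above the null value, so the width might have been picked to clear 90%. The protocol documents neither. All that can be said is that 2.4 mentions no null value and no power.

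Alpha, the form of the test and the interval method are commonly left to the statistical analysis plan, so their absence is no finding. It does mean that the power figures are conditional. At 50% prevalence and one-sided 0.05 they run from 15% to 41% by test variant and evaluable number, so 15% to 24% should not be quoted without its assumptions. The lowest value also needs the 55-evaluable reading, whereas Sections 2 and 2.3 aim for 60 usable or completed recordings and 2.5.3 allows a repeat Holter. This stands, but only in part: the reproduced formula already contains the 8%, which implies about 55 evaluable, and at 60% to 70% prevalence the two readings nearly agree.

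Two stronger readings fail. One is that rejection may well be impossible. The exact 0.05 test cannot reject with 28 or fewer AF-positive subjects, and the chance of that is 35% (60) or 61% (55) at 50% prevalence, but only 1% or 6% at 61.9%. The other is that the expected sensitivity would usually fail whatever the test. At one-sided 0.10 that is untrue in several of the cases computed.

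Finally, a normal-approximation half-width is a customary planning input, and 2.4 does not promise it as the reported interval. It is nevertheless printed as the precision of a 95% interval, and at this size and sensitivity it is not.

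This is a post-market observational study of a cleared device, and the protocol makes no treatment decision depend on rejection. That limits the consequences but leaves the statement in 2.4 wrong.

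**Conclusion.** The point holds as a mismatch between the criterion used for sizing and the primary test, with two consequences.

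- **Precision.** The stated 6.35% is not what 28 to 30 AF-positive subjects deliver at 97% sensitivity. About 8 points of half-width, and 13 to 14 points on the lower side, is the realistic expectation.
- **Power.** At one-sided 0.05 or 0.025 and the stated 50% prevalence, a device with the expected sensitivity is more likely than not to leave the null hypothesis unrejected. This holds for every test variant considered: none exceeds 41% at 0.05, and none can gain power at the stricter level. With an exact test at those two levels it holds at every prevalence computed from 50% to 70%.

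It does not extend to every setting: mid-p at 0.05 with 60 evaluable reaches 55% at 70% prevalence, and at 0.10 power runs from 41% to about 68%. All of these figures take Holter-AF-positive subjects as the denominator.

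**What to change.** No added enrolment is needed.

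1. In 2.4, replace the 6.35% precision with the expected precision of an exact or Wilson 95% interval at 28 to 30 AF-positive subjects. For the exact interval this is a half-width of about 8.0 to 8.4 points and a lower limit on average 13 to 14 points below the estimate.
2. In 2.4, say that the listed calculation concerns interval precision and gives no power for the test in 2.5.1. Then state that test's power at 97% sensitivity, averaged over the AF-positive count, with the alpha, test form, prevalence and evaluable number it assumes. The 40% that applies at exactly 30 AF-positive subjects should not stand alone.
3. In 2.5.1, report sensitivity with the same exact or Wilson 95% interval beside the test.

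The cost is wording in two sections, with no further subjects, visits or data. The downside is that the stated precision becomes less favourable and the low power is disclosed. The change does not raise the power.
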